## 11.2 Statistical Analysis Plan

Descriptive statistics will be used to summarize the demographic and baseline characteristics of the study population. Subjects who do not complete the required observations will be described and evaluated separately, as necessary. Reasons for study discontinuation and date of withdrawal from study will be described

The binomial proportion and its 95% confidence interval will be used to estimate the objective (complete + partial) response rate as defined in Section 8.0. With 12 patients at the maximally treated dose, the response rate can be estimated with a 95% confidence interval with width no greater than  $\pm 28.3\%$ .

The effects of PTC299 on serum and plasma VEGF, VEGFR and cytokine profiles will be evaluated by comparing the Day 28 value with the pre-treatment value, and the Day 28 value with the lowest value obtained subsequent to Day 28. These changes will be evaluated using the paired t-test, or if the data are not normally distributed, the Wilcoxon signed rank test. Comparisons between dose levels with respect to these changes will be evaluated using ANOVA or the Kruskal-Wallis test if the data are not normally distributed.

Comparisons of on-treatment values with the pre-treatment baseline value, and with the corresponding baseline value within each cycle will be performed using paired t-tests. If the distribution of the data deviates substantially from normality, the analysis will be performed on log-transformed data. Differences in change from baseline among dose levels will be analyzed by means of ANOVA (including a test for linear dose response); if a significant effect is observed, individual comparisons among dose levels will be performed with t-tests. The pattern of responses across doses will be considered in interpreting the logical validity of the results. Results will be presented in tabular and graphic form, as appropriate.

Immunohistochemistry (IHC) will be used to determine expression of the following: VEGF, VEGFR-2, VEGFR-3, phospho-Akt, KSHV LANA, orf59, p53 and HIF-1 $\alpha$ . We will count the number of positive cells per HPF for a total of 10 fields per section and derive an index value. We will consider a 50% change from baseline in the index value for the aforementioned markers a biological response. For each measure (VEGF, VEGFR-2, VEGFR-3, phospho-Akt, KSHV LANA, orf59, p53 and HIF-1 $\alpha$ ), we will estimate the proportion of patients who demonstrate a 50% change between baseline and on treatment (between day 22 and day 28) value. The exact binomial 95% confidence interval will be derived for each measure.

To evaluate the effects of PTC299 on tumor cell proliferation, the change in immunohistochemistry of Ki67 from the pre-treatment to the post-treatment biopsy will be tested using the Wilcoxon sign test to determine if the change is less than zero, suggesting a decrease. To evaluate the drug's effects on circulating concentrations of angiogenic factors and cytokines, HIV and KSHV loads, and T-lymphocyte subsets, changes in these levels from pre-treatment to indicated sampling times will be tested by repeated-measures ANOVA, single and multivariate analysis.

For each subject, study drug administration will be described in terms of the actual doses administered and the proportion of drug actually delivered relative to the amount that should have been delivered. The total number of cycles administered; the median (range) of cycles administered; dose modifications, dose delays, and dose omissions; and reasons for deviations from planned therapy will be described by starting dose level. The type and timing of use of concomitant drugs will also be described.

AEs and laboratory abnormalities will be summarized by type and severity grade. First-cycle DLTs, adverse events leading to death or to discontinuation from treatment, and serious adverse events will be considered with special attention.

Pharmacokinetic parameters will be calculated using the actual sample collection times. Pharmacokinetic variables will be calculated from the plasma concentration data using standard compartmental and noncompartmental methods, as appropriate for the data. Variables of interest may include  $T_{max}$ ,  $C_{max}$ ,  $C_{24h}$ ,  $AUC_{0-24}$ , and  $t_{1/2}$ . Plasma concentrations and PK parameter results will be presented in tabular and graphic form by dose level and

time period (Day 1 and Day 28). Modeling of the PK data may be performed using noncompartmental and compartmental models, as appropriate.

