When there is a dose modification, the subject should be notified of the change in dose and the appropriate clinic staff should instruct the subject about the revised number of study medication capsules to be used per dose according to the new dose level.

Clinical use of other anti-VEGF compounds (e.g., bevacizumab) can be associated with delayed wound healing. For this reason, subjects who require surgery or a deep invasive procedure should have PTC299 held for  $\geq 2$  weeks before the procedure, if possible, and PTC299 should be held for  $\geq 2$  weeks after the procedure, or until complete wound healing, to avoid the theoretical risk of impaired wound closure.

#### 5.3.5 Treatment in Phase 2

Once the safety profile at each dose level has been established based on first cycle DLTs in Phase 1, up to 21 additional subjects whose response to treatment can be evaluated will be enrolled in the Phase 2 portion of the study at the highest safely tolerated dose established in the Phase 1 portion to better define the safety, antitumor activity and biological activities of PTC299 at this dose level. In the Phase 2 portion of the study, Simon's 2-stage design will be used, as described in Section 11.1. Treatment will consist of 4 week cycles of therapy (56 or 84 doses) as described in Section 5.3.2. The maximum duration of treatment is 12, 4-week cycles. Definitions of DLT will be as described in Section 5.3.3. Study drug interruptions and dosage reductions will be managed as described in Sections 5.3.1 and 5.3.4.

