**Table 6. Probability of Dose Escalation within Stage (Stage 1 & Stage 3)**

True Incidence of DLT	Probability of Escalating
10%	0.91
20%	0.71
30%	0.49
40%	0.31
50%	0.17
60%	0.08

Abbreviations: DLT = dose-limiting toxicity

Thus, if the true underlying proportion of DLTs is 20% at the current dose level, there is a high probability (0.71) of dose escalation to the next dose level. Conversely, if the true underlying proportion of DLTs is 50% at the current dose level, there is a low probability (0.17) of escalation to the next dose level.

In the Phase 2 portion of the study, Simon's 2-stage design is used to test the null hypothesis that the response rate (CR + PR) is  $\leq 10\%$  against the alternative that it is  $35\%$  at the one-sided 0.05 significance level with power of 0.90. Eleven subjects will be enrolled at the first dose level administered in Phase 2 (eg, 100 mg/dose BID) considering subjects from both the Phase 1 and Phase 2 portions of the study. If  $\leq$  one out of 11 subjects respond, the study will be stopped. If  $\geq$  two out of 11 subjects respond, the study will enroll 18-21 additional subjects in Stage 3. Assuming that the true response rate is  $\leq 10\%$ , the probability of stopping the trial at the end of Stage 2 is 0.697. However, if the true RR is  $\geq 35\%$ , then there is only a probability of 0.059 that the trial will be stopped erroneously in Stage 2.

Using the proposed dose escalation scheme from 100 mg/dose BID to 160 mg/dose TID, the probability of dose escalation based on the true rate of DLT at the lower dose, is given in Table 7 below:

**Table 7. Probability of Dose Escalation  
(100 mg/dose BID to 160 mg/dose TID)**

True Incidence of DLT	Probability of Escalating
10%	0.96
20%	0.82
30%	0.59
40%	0.35
50%	0.18
60%	0.08

Abbreviations: DLT = dose-limiting toxicity

Thus, if the true underlying proportion of DLTs is 20% at the 100 mg/dose BID dose level, there is a high probability (0.82) of dose escalation to the next dose level. Conversely, if the true underlying proportion of DLTs is 50% at the 100 mg/dose BID dose level, there is a low probability (0.18) of escalation to 160 mg/dose TID.

At the end of Stage 3, if  $\geq 6$  subjects respond, then the null hypothesis that the true response probability is  $\leq 10\%$  will be rejected, and further investigation of PTC299 in this patient population is warranted.

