In Stage 3, a minimum of 12 patients will be treated at the maximally treated dose. If the underlying response rate is no greater than 10%, then the probability of observing 4 or more responses among 12 patients will be  $< 5\%$ . Thus, if there are 4 or more responses among 12 patients, it can be inferred that the response rate is  $> 10\%$ .

The minimum number of subjects to be entered in the study is **three** (i.e., if  $\geq$  two subjects experience DLT at the lowest dose level in Stage 1).

The maximum number of evaluable subjects to be enrolled in the study is **38** (i.e., 9 subjects have been enrolled into Stage 1, 8 subjects have been enrolled into Stage 2, and up to 21 subjects will be enrolled to Stage 3). Assuming that  $\sim 15\%$  of subjects will not be evaluable for response, we estimate that the maximum number of subjects in the study will be **44**.

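### The denominator of the primary response rate is not named; if only response-evaluable subjects are counted, the rate and the type I error can be biased upward

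*Combined protocol and SAP*

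**What the plan says.** Estimating the response rate is a primary objective (Section 2.1.3). The Schema and Section 3.3.1 give the sample as 3 to 38 evaluable subjects, and the Schema allows up to 44 enrolled to reach 38. Section 11.1 explains the difference: it assumes that about 15% "of subjects will not be evaluable for response, we estimate that the maximum number of subjects in the study will be" 44. Section 5.3.5 describes the Phase 2 cohort in the same terms: "up to 21 additional subjects whose response to treatment can be evaluated will be enrolled".

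The decision rules are in Section 11.1. "In the Phase 2 portion of the study, Simon's 2-stage design is used to test the null hypothesis that the response rate (CR + PR) is" at most 10%, against 35%, "at the one-sided 0.05 significance level with power of 0.90". For the first look, "Eleven subjects will be enrolled at the first dose level administered in Phase 2". With at least two responders among the 11, "the study will enroll 18-21 additional subjects in Stage 3". The null is rejected at six or more responders. A separate statement for Stage 3 infers a rate above 10% from four or more responses among 12 patients at the top dose.

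Section 11.2 estimates the response rate by a binomial proportion with a 95% confidence interval. On incomplete data it says only: "Subjects who do not complete the required observations will be described and evaluated separately, as necessary". No section defines evaluable for response, names an analysis population for the rate, or says how a subject with no post-baseline assessment is counted.

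**The concern.** Enrolling 44 to obtain 38 response-evaluable subjects makes sense only if the evaluable subjects form the denominator. On that reading, a subject who leaves before any post-baseline tumour assessment drops out of the rate.

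Such a subject is unlikely to be a responder. The first scheduled on-treatment tumour assessment is Day 29 (Sections 4.2.1.1 and 8.0). CR, and PR by lesion count, must last at least four weeks (Section 8.1). Leaving these subjects out would then remove mainly non-responders. A single-arm trial has no comparator in which the same selection could cancel. At stake are the primary estimate and the decision whether PTC299 warrants further study.

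**Working it through.** **Inputs.** From Section 11.1: null 10%, alternative 35%; continue with at least 2 of 11; 18 to 21 further subjects, so N = 29 to 32; reject at 6 or more; separate rule of 4 of 12; 15% not evaluable. The response rate among non-evaluable subjects is not in the documents, so it is varied.

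**The plan's own figures**
- Enrolment: 38 × 1.15 = 43.7, giving the stated 44. Dividing instead, 38 / 0.85 = 44.7, giving 45.
- Early stopping at 10%: 0.9^11 + 11 × 0.1 × 0.9^10 = 0.3138 + 0.3835 = 0.697, as stated. At 35% the result is 0.061; the plan states 0.059.
- P(at least 4 of 12 at 10%) = 0.026, consistent with the stated <5%.

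**Baseline of the two-stage rule.** With X1 ~ Bin(11, p) and X2 ~ Bin(N − 11, p), P(reject) = Σ over x from 2 to 11 of P(X1 = x) × P(X2 ≥ 6 − x). At p = 0.10 this is 0.051 at N=29 and 0.070 at N=32, before any exclusion.

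**Effect of exclusion.** Let d be the share not evaluable and f their response rate relative to evaluable subjects. If the rate among all treated is 10%, the rate among evaluable subjects is 0.10 / ((1 − d) + d × f). With d = 0.15 and f = 0 this is 0.10 / 0.85 = 11.8%. Putting that rate into the same formula:

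| Left out (d) | Relative response (f) | Rate among evaluable | ≥6 rule, N=29 | ≥6 rule, N=32 | ≥4 of 12 |
|---|---|---|---|---|---|
| 0% | – | 10.0% | 0.051 | 0.070 | 0.026 |
| 15% | 1 | 10.0% | 0.051 | 0.070 | 0.026 |
| 15% | 0.5 | 10.8% | 0.069 | 0.093 | 0.033 |
| 5% | 0 | 10.5% | 0.062 | 0.085 | 0.030 |
| 10% | 0 | 11.1% | 0.077 | 0.103 | 0.036 |
| 15% | 0 | 11.8% | 0.095 | 0.126 | 0.044 |

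In the last row the early-stopping probability falls from 0.697 to 0.623. The 4-of-12 rule passes 5% only at about 20% left out (0.053, with f = 0).

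**Effect on the reported rate.** 29 / 0.85 = 34.1, so about 35 treated: 6/29 = 20.7% becomes 6/35 = 17.1%. For the smaller rule, 12 / 0.85 = 14.1, so about 15 treated: 4/12 = 33.3% becomes 4/15 = 26.7%.

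**What a new denominator does to the rule.** The cutoff is a count of responders, so changing the denominator corrects the estimate but does not by itself restore 0.05. Keeping 11 in the first stage and setting p = 0.10 in the formula above, the cutoff of 6 gives 0.090 at 35 treated and 0.111 at 38 treated (32 / 0.85 = 37.6). A cutoff of 7 gives 0.038, 0.042 and 0.047 at 34, 35 and 36 treated, but 0.052 and 0.057 at 37 and 38.

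**The case against.** The strongest reply is that the documents never say the rate and thresholds use evaluable subjects only. A reader might infer this as a stated rule, but the evaluable wording appears in sample-size and enrolment text. The thresholds are written for subjects enrolled (11), treated (12) or responding (6), and the 11 are not called evaluable. Section 8.0 says all subjects will be evaluated for response. The sentence on incomplete observations stands in a paragraph on baseline characteristics and disposition, and does not say these subjects leave the denominator.

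A reader might also infer that subjects who stop for progression or toxicity are removed. That is not supported. Progressive disease is a defined response category (Section 8.1.4), so a progressor has been evaluated. Section 4.3.6 requires a tumour assessment at discontinuation, and Section 4.4 another 30 days later. Those with none should be mainly subjects lost or withdrawn before any is done.

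Nor is there a written rule that drops and replaces subjects for missing response. Section 3.3.3 covers failure to complete cycle 1 and DLT evaluability, and bars replacing subjects withdrawn for PTC299-related DLT. Finally, a reader might apply the cutoff of 4 to the 15 subjects planned at the top dose in Section 3.3.1; the written rule is 4 of 12.

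All of this stands, and it limits the claim. It does not close the gap. Despite the assessments required, the plan itself expects about 15% not to be evaluable for response, enrols extra subjects to offset them, and does not say how they are counted.

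**Conclusion.** The point holds as a conditional one. The denominator of a primary endpoint is undefined, and the natural evaluable-only reading can bias the rate and the type I error upward. The worst case adds about 4.4 percentage points to the type I error at N=29 (0.095 − 0.051) and 5.6 at N=32 (0.126 − 0.070).

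These figures rest on three assumptions: evaluable subjects are the denominator, the full 15% is left out in both parts of the design, and none of those left out would have responded. With half the relative response the figures are 0.069 and 0.093. With non-informative exclusion there is no inflation.

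It would be wrong to attribute all the excess over 0.05 to the denominator, because the cutoff of 6 already gives 0.051 to 0.070 with no one left out. The 4-of-12 rule keeps its stated bound at 15%.

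**What to change.** In Section 11.2:
- Make the primary response analysis all eligible subjects who took at least one dose at the relevant level, and count those with no post-baseline response assessment as non-responders.
- Define evaluable for response, separately from evaluability for DLT in Section 3.3.3.
- Keep the evaluable-only rate as a sensitivity analysis.
- Report the exact type I error of the rejection rule at the number actually treated. A fixed new cutoff of 7 is not a safe substitute: it holds 0.05 only up to 36 treated, and the plan's 15% could imply 37 or 38 (32 × 1.15 = 36.8; 32 / 0.85 = 37.6). It would also change a decision rule after the subjects of Stages 1 and 2 have been enrolled.

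The cost is a few sentences and one extra table. The reported response rate may be slightly lower.

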## 4.2 Evaluations During Treatment

Evaluations may occur up to 3 days before or after the end of the study visit indicated, unless otherwise noted. Each cycle will be 28 days. Evaluations will continue as outlined below.

- 4.2.1 Clinical assessment at Days 15 ( $\pm$  2) of cycle 1, and then Day 1 on cycle 2 and every cycle thereafter to include an assessment of the following at every visit unless otherwise specified:
- 4.2.1.1 KS tumor assessment Day 1 of cycle 2 and every cycle thereafter. Response of KS to treatment will be assessed as described in Section 8.0. Photographic documentation of lesions will be completed at each visit when the KS response category changes. For example, if a participant's KS response category changes from no response (stable disease) to partial response, the site will take photos of this to document the category change. If there was no change in the KS response category, no photos are required. Refer to Appendix XIV for lesion photography guidelines.
  - 4.2.1.2 A complete physical exam including: vital signs, weight, Karnofsky performance status (Appendix II) and toxicity evaluation.
  - 4.2.1.3 Signs and symptoms review.
  - 4.2.1.4 Complete blood count with differential and platelets.
  - 4.2.1.5 INR and aPTT.
  - 4.2.1.6 Serum chemistries: liver enzymes (AST, ALT, alkaline phosphatase), BUN, creatinine, electrolytes (sodium, potassium, chloride, bicarbonate), calcium, phosphorus, glucose, total protein, albumin, bilirubin (direct and indirect), triglycerides and total cholesterol. If the triglycerides and/or total cholesterol increases to  $\geq$  grade 3, then these values should be rechecked in a fasting state and the cholesterol fractionated.
  - 4.2.1.7 Urinalysis
  - 4.2.1.8 For women of childbearing potential: serum  $\beta$ -HCG at any time pregnancy is suspected.
  - 4.2.1.9 All HIV-related and AIDS-defining events (Appendix XII) and concomitant prescription and over the counter medications, vitamins and supplements taken since the last visit.
  - 4.2.1.10 CD4 count on Day 29 (Day 1 of cycle 2) and every three cycles (12 weeks) thereafter.
  - 4.2.1.11 Plasma HIV-1 RNA on Day 29 (Day 1 of cycle 2) and every three cycles (12 weeks) thereafter.
  - 4.2.1.12 KSHV viral load on Day 29 (Day 1 of cycle 2) and every three cycles (12 weeks) thereafter.

4.2.1.13 Blood for ACTH and cortisol on Day 29 (Day 1 of cycle 2) and every cycle thereafter.

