#### 4.2.3 Pharmacokinetics of PTC299

Blood for PK assessments should be collected immediately pre-dose; and at 1, 2, 3, 4, 5, 6, and 8 hours after the AM dose on Day 1 and again at 1, 2, 3, 4, 5, 6, and 8 hours after the AM dose on Day 28 of cycle 1. (**Note:** the Day 28/cycle 1 PK samples can be collected up to 3 days prior to Day 28). A PK sample will also be collected prior to the AM dose on Day 15 ( $\pm$  1 day) during cycle 1 and prior to the AM dose on Day 28 of cycle 2 (or Day 1 of cycle 3 if the subject's last dose of study treatment was the evening prior). Blood samples for PTC299 PK assessments will not be collected after cycle 2. The actual sample collection times should be recorded. Please see Appendix IX for detailed collection, processing, storage and shipping instructions for PK samples.

4.2.4 Assaying secreted cytokines characteristic for KS: To measure PTC299's effect on KS we will evaluate serum and plasma for levels of the cytokines (e.g., VEGF-A, VEGF-C, VEGF-D, VEGF-R1, VEGF-R2, VEGF165b, PlGF, IL-6, and IL-8) at baseline (pre-dose of study treatment on Day 1) and mid-cycle (Day 15) of cycle 1, on Day 1 of all subsequent cycles, and at the time of treatment discontinuation and 30 days post discontinuation of study therapy. Please see Appendix IV for detailed collection, processing, storage and shipping instructions for these samples. Depending on the results of these assays, other potential serum markers characteristic for KS may also be measured.

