## 5.3 Dosing

### 5.3.1 PTC299 Treatment

Each cycle with the study drug includes administration of 56 to 84 doses of PTC299 during a 4-week (28-day) period. The maximum duration of treatment is 12, 4-week cycles. PTC299 will be administered on a BID or TID schedule at approximately the same times each day. At each dose administration, the capsule number corresponding to the appropriate dose level of PTC299 is to be swallowed whole with a glass of tap water (150 to 200 mL). Subjects should be instructed not to bite or chew on the capsules. In case of breakage of the capsules in the oral cavity, an additional glass of water should be taken immediately.

On Day 1 and on Day 28 of cycle 1, the drug will be administered in the clinic with dosing appropriately timed relative to blood sampling for PTC299 PK. Thereafter, subjects will be given an adequate supply of capsules to take at home for the duration of each single cycle (28 days) of treatment.

Ideally, when given BID, doses should be taken at ~12-hour intervals (e.g., at ~7:00 AM and at ~7:00 PM) and, when given TID, PTC299 doses should be taken at ~8-hour intervals (eg, at ~7:00 AM, at ~3:00 PM, and at ~11:00 PM). If convenient for the subject, the drug may be taken during or within ~30 minutes after a meal; however, administration with food is not required. Yogurt or pudding may be taken together with the capsules in case of difficulty in swallowing. While it is realized that variations in dosing schedule may occur in the outpatient setting, the prescribed regimen (dosing intervals) should be followed as closely as possible, especially in the clinic. In particular, on study days of PK profiling, patients administered TID dosing should take the first dose immediately after the pre-dose blood draw and not dose again until all profile blood draws are completed.

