## **7.0 CRITERIA FOR DISCONTINUATION**

- Study medication will be interrupted or permanently discontinued for treatment related toxicities as outlined in Section 5.3.3.
- Disease progression.
- Subjects who show no more than stable disease after six 4-week cycles of treatment will be permanently removed from treatment.
- Subjects who show a partial response will be treated for up to twelve 4-week cycles.
- Subjects who show a complete response will be treated for two 4-week cycles beyond confirmation of complete response.
- Subjects who become pregnant or breast-feed or who require systemic chemotherapy for the treatment of a malignancy other than KS.
- Subjects who require treatment with medications which are disallowed as outlined in Section 5.4.2.
- Subjects who are noncompliant with respect to taking drugs, keeping appointments or having tests required for the evaluation of drug safety and efficacy.
- Subjects have the right to withdraw from the study at any time for any reason.
- The Investigator has the right to remove subjects from the study for clinical reasons which he/she believes are life threatening to the subject even if such reasons do not fall into the toxicity classifications discussed above.

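### The test of Day 28 against the lowest later cytokine value is biased toward a further fall, and its false-positive rate is far above 5% at the planned top-dose cohort size

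*Combined protocol and SAP*

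**What the plan says.** Section 11.2 plans two within-subject comparisons for serum and plasma VEGF, VEGFR and cytokines. One is Day 28 against pre-treatment. The other is "the Day 28 value with the lowest value obtained subsequent to Day 28". The next sentence covers both: "These changes will be evaluated using the paired t-test", with the Wilcoxon signed rank test if the data are not normal. Dose levels are then compared on the same changes: "Comparisons between dose levels with respect to these changes will be evaluated using ANOVA or the Kruskal-Wallis test". Nothing allows for the selection of a minimum or fixes how many later samples enter it.

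Section 4.2.4 schedules samples pre-dose on Day 1 and on Day 15 of cycle 1, then "on Day 1 of all subsequent cycles, and at the time of treatment discontinuation and 30 days post discontinuation of study therapy". On treatment length, Section 5.3.1 says "The maximum duration of treatment is 12, 4-week cycles", and Section 7.0 says "Subjects who show no more than stable disease after six 4-week cycles of treatment will be permanently removed from treatment".

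Section 11.2 also plans a separate analysis of these markers in which "changes in these levels from pre-treatment to indicated sampling times will be tested by repeated-measures ANOVA". It is additional to the lowest-value test and does not replace it.

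**The concern.** A paired test of zero mean difference is valid only if the two quantities compared have the same expectation when there is no effect. A single Day 28 value and the smallest of several later values do not. Each extra later sample gives another chance of a low reading, so the minimum drifts down with the number of samples even for an inert drug. Using Wilcoxon or log-transformed data does not help, because the shift is in the quantity being tested.

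Effects on circulating VEGF, VEGFR and cytokines are a secondary objective (Section 2.2.2), and Section 1.2.5.3 suggests that falls in circulating tumor-derived VEGF may be evidence of activity in patients. A significant result here could be taken as a drug effect that deepens after cycle 1, and it could disagree with the sound analyses planned beside it. The between-dose comparison has a related weakness: if subjects at one dose stay on treatment longer, they supply more later samples and show a larger built-in fall.

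**Working it through.** The documents give no error rate or power for this test, so there is no stated figure to reproduce.

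**Number of later samples, k.** There is no separate Day 28 cytokine sample. The nearest is Day 29 (Day 1 of cycle 2), taken here as the Day 28 value.

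- Stop in cycle 2: discontinuation + 30-day sample = 2.
- Removed as stable after six cycles: Day 1 of cycles 3 to 6 (4) + 2 = 6.
- Twelve cycles: Day 1 of cycles 3 to 12 (10) + 2 = 12.

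**Number of subjects, n.** 3 per Stage 1 cohort (Section 3.3.1); at least 12 (Section 11.1) and a planned 15 (Section 3.3.1) at the top dose.

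**Model.** No change after Day 28, equal variance at all visits, d = min(later values) − Day 28 value. A constant subject effect cancels in d. The level is two-sided 5%, which is an assumption because the plan sets none for these tests.

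**Hand check, independent visits, k = 2, n = 12**, in visit-level SDs:

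- Mean of d = −1/√π = −0.564.
- Variance of d = 1 + (1 − 1/π) = 1.682, so SD = 1.297.
- Expected shift in standard errors = 0.564 / (1.297/√12) = 1.51.
- A t-test on 11 degrees of freedom (critical value 2.20) with noncentrality 1.51 rejects about 28% of the time. This treats d as normal.

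For k = 6 the mean is −1.267 and the SD 1.190, so the shift is 1.267 / (1.190/√12) = 3.69 standard errors and the rejection rate about 92%.

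**Simulation of the paired t-test (20,000 replicates), n = 12 to 15:**

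| Later samples | Built-in fall, independent (SD) | False positives, independent | Built-in fall, lag-1 correlation 0.8 (SD) | False positives, correlation 0.8 |
|---|---|---|---|---|
| 1 | 0 | 5% | 0 | 5% |
| 2 | 0.56 | 28-35% | 0.25 | 19-24% |
| 6 | 1.27 | 92-97% | 0.76 | 79-89% |
| 12 | 1.63 | over 99% | 1.13 | 97-99% |

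Nearly all rejections are toward a fall. The row for one later sample has the correct size, which shows that taking the minimum is the cause.

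**Variations:**

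- Wilcoxon, independent visits: 25-33%, 90-97% and 99% for 2, 6 and 12 later samples.
- Leaving out the 30-day sample (1, 5 or 11 later samples): 5%, 86-94% and over 99% if independent; 5%, 71-82% and 96-99% at correlation 0.8.
- Three subjects, 2 to 12 later samples: 8-29% if independent, 6-19% at correlation 0.8.
- Mixed follow-up, n = 12 to 15, correlation 0 to 0.8, k drawn with equal weight from an assumed list: 37-62% if most stop early {2,2,2,3,4,6}; 70-92% if centred on six-cycle removal {2,3,4,6,6,6,8,12}; 86-98% if most stay long {4,6,6,6,8,12,12}.

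**Between-dose ANOVA, 11 against 15 subjects** (the planned numbers at 100 mg BID and at the top dose): 5% with equal follow-up; 27-31% if every subject has 2 later samples at one dose and 6 at the other; 12-15% for 6 against 12. With the mixes above, early against middle gives about 11% and middle against late about 7%.

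**After the change.** Testing one prespecified later visit, or the mean of the later values, gives 4.8-5.3% for n = 3, 12, 15 and 38.

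**The case against.** The case for leaving this alone is that the objective is to describe effects, no significance level is set for these tests, and no escalation, stopping or activity decision uses them. Sound analyses of the same markers are planned: Day 28 against pre-treatment, on-treatment against baseline, and the repeated-measures ANOVA. The most alarming figures are also extremes. Twelve later samples for everyone would require a whole cohort treated for twelve cycles, although stable subjects leave after six and complete responders stop two cycles after confirmation. The 27-31% between-dose figure requires complete separation of follow-up, and the documents give no evidence that follow-up will differ by dose. In a cohort of three with two later samples the excess is slight.

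Most of this limits the size and consequence of the problem and should be reported with it. The 12-sample row and the 2-against-6 comparison should be read as upper bounds, and the mixed-follow-up figures as illustrations. Section 11.2 also does not say whether the paired test is run by dose or pooled, so 12 to 15 is a choice; at n = 38 with 2 later samples the rate is about 75% (independent visits).

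None of it removes the bias. The plan specifies a p-value for this comparison whatever the objective is called, and the other analyses stand beside that p-value without replacing it.

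**Conclusion.** The concern holds. As written, the test has the wrong null value whenever subjects have two or more later samples, and it favours a further fall after Day 28. At 12 to 15 subjects, with follow-up centred on six-cycle removal, an inert drug would give a significant result about 70-92% of the time instead of 5%. The excess is clear from about six subjects upward (14% with 2 later samples, 56% with 6, independent visits) and small for three subjects with two later samples.

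The figures assume a two-sided 5% level, no time trend, normal values of equal variance and the stated correlations. A true rise after Day 28 would offset part of the bias. The between-dose test is distorted only if follow-up differs by dose.

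Day 28 against pre-treatment, on-treatment against baseline, the repeated-measures ANOVA, and the safety, MTD and response conclusions are unaffected. This should be corrected, but it does not threaten the trial's main conclusions.

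**What to change.** In Section 11.2:

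- Remove the p-value for Day 28 against the lowest later value, and the between-dose test of that change.
- Report the lowest value descriptively: its value, the visit at which it occurred and the number of later samples. State whether the 30-day off-treatment sample can count.
- Keep the planned test of Day 28 against pre-treatment.
- Assess later change at one or two prespecified visits, or by extending the planned repeated-measures ANOVA to a mixed model on log concentration with visit as a factor. The prespecified visits alone would cure the defect. Either way, state that later on-treatment visits include only subjects still being treated.
- Name the Day 29 (Day 1 of cycle 2) sample as the Day 28 value. The window in Section 4.2 ("Evaluations may occur up to 3 days before or after the end of the study visit indicated") covers Day 28, so this is mainly labelling. It also makes clear that this sample is not among the later ones; if it were, the difference could never be positive.

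The cost is SAP wording only. The same samples and assays are used.
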